We will test our central hypothesis in a randomized controlled trial (RCT) designed to determine if reduced insomnia symptoms result in improved CVD risk among those with co-morbid PTSD and Insomnia Disorder (ID). Specific and established CVD morbidity and mortality biomarkers of risk will be examined, including vascular endothelial function measured by brachial artery flow-mediated dilation (FMD), nighttime blood pressure (BP) dipping measured using 24-hour ambulatory blood pressure monitoring (ABPM), arterial stiffness measured by central pulse wave velocity (PWV), and atherosclerotic cardiovascular disease (ASCVD) risk score (Bonnet & Arand, 2007; Bonnet & Arand, 2010; Routledge & McFetridge-Durdle, 2007; Tsuji et al., 1996; Verdecchia, Angeli, Gentile, Mazzotta, & Reboldi, 2011). Insomnia will be measured *via* a multi-modal assessment strategy, including self-report and actigraphy. The *rationale* for the proposed research is if it is established that insomnia-related sleep impairment is a modifiable CVD risk factor among those with PTSD, new innovative approaches to integrating sleep treatment with PTSD focused interventions can be developed and implemented.

We will randomize 150 individuals with co-morbid PTSD and ID to either an 8-week CBT-I intervention or to a minimal contact control condition. Insomnia severity and objective sleep parameters, quality of life measures, and biomarkers of CVD risk will be assessed at baseline, post-intervention, and at a 6-month follow-up. Specific Aims include:

AIM 1: Determine whether CBT-I improves (a) CVD risk biomarkers, (b) 10-year ASCVD risk, and (c) quality of life (QoL) in persons with PTSD. *Hypothesis 1:* Compared to the control condition, CBT-I will be associated with increased sleep-efficiency and decreased insomnia severity (manipulation check), improved CVD risk biomarkers (Hypothesis 1a) including (i) lower nighttime BP and enhanced nighttime BP dipping, (ii) augmented vascular endothelial function (FMD), (iii) reduced sympathetic nervous system (SNS) activity (catecholamines), lower 10-year ASCVD risk score (Hypothesis 1b) and improved quality of life (Hypothesis 1c).

AIM 2: Determine whether within-person changes in sleep efficiency are accompanied by improved CVD risk biomarkers and 10-year ASCVD risk. *Hypothesis 2:* Within-person improvements in sleep efficiency (N=150) will be associated with improvements in CVD risk biomarkers and reduced ASCVD risk score.

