B.6.3 24-hour Urinary Catecholamines (Epinephrine and Norepinephrine). The SNS is involved in the pathogenesis of hypertension, as well as various manifestations of CBD (Esler, Lambert, Schlaich, & Navar, 2010; Grassi, Mark, & Esler, 2015). SNS activity can be assessed noninvasively by the measurement of catecholamines (epinephrine and norepinephrine) excreted in the urine. Using 24-hour urinary catecholamine assays, partitioned in awake and nighttime sleep-period samples, our own work has shown that blunted nighttime BP dipping is related to nighttime SNS hyperactivity in men and women with hypertension ([name], Steffen, Blumenthal, Kuhn, & Hinderliter, 2002; [name] et al., 2011). Data from the Multi-Ethnic Study of Atherosclerosis (MESA) suggest that heightened SNS activity is linked to low sleep efficiency (Castro-Diehl et al., 2016). SNS hyperactivity assessed by 24-hour urinary catecholamine excretion has been found to be associated with low sleep efficiency, measured by actigraphy, in healthy middle-aged men and women (Zhang et al., 2011). These observations are consistent with our hypothesis that SNS hyperactivity is a potential mechanism of CVD risk related to low sleep efficiency. Urinary catecholamines have also been used to document that insomnia disorder is often characterized by a state of hyperarousal (Roehrs & Roth, 2016).

B.6.. 10-year Atherosclerotic Cardiovascular Disease (ASCVD) Risk. ASCVD risk will be based on the Pooled Cohort Equations recently validated and recommended by the clinical practice guideline expert panel of the American College of Cardiology/American Heart Association (Goff et al., 2013). These equations estimate the 10-year risk of a primary ASCVD event (including myocardial infarction and stroke) among patients without pre-existing CVD who are between 40 and 79 years of age. Patients are considered to be at "elevated" risk if the Pooled Cohort Equations predicted risk is $\geq 7.5\%$. Because several large population studies have shown that insomnia and short sleep duration are linked to hyperlipidemia (Lin, Tsai, & Yeh, 2016), the CBT-I intervention holds promise for both lowering BP and improving the abnormal lipid profiles seen in PTSD (Solter, Thaller, Karlovic, & Crnkovic, 2002).

C. RESEARCH DESIGN AND METHODS

Figure 1. Study Design

C.1. Study Design Overview

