In an innovative use of an established and well validated intervention for insomnia, we propose to examine the direct effects of sleep on biomarkers of CVD risk outcomes among persons with PTSD and comorbid insomnia disorder (ID; see Figure 1). In this 2-arm RCT, 150 participants with PTSD and ID will be randomized at a 2:1 ratio to either CBT-I, or a minimal contact control condition (CCC). We anticipate that we may need to consent and screen as many as 500 participants to reach this goal. Sleep efficiency as measured by actigraphy will be the primary sleep outcome measure. Other parameters [total sleep time (TST) wake after sleep onset (WASO), sleep fragmentation] will be measured with a multi-modal assessment strategy including validated self-report measures, sleep diaries collected *via* Qualtrics, and objective sleep measurement (i.e., actigraphy). Sleep diaries and actigraphy will be continuously collected for 10-weeks (including a week-long baseline, 8-week period for CBT-I or CCC, and one-week post treatment) and for a week-long period at the 6-month follow-up. The primary outcomes for this clinical trial are established biomarkers of CVD risk, including flow mediated dilation, SNS activity, nighttime BP, nighttime BP dipping, and ASCVD risk. These biomarkers will be assessed at three time points: baseline, post-intervention (8-weeks), and 6-month follow-up. The 6-month follow-up period will allow us to evaluate whether the intervention effects on CVD risk are sustained beyond the immediate post-intervention period. Timing for the 6-month follow-up visit will be 6 months after

the baseline assessment or three months after the post-intervention assessment, whichever is later. Participants in both arms will continue with usual medical care.

C.2. Recruitment

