C.6.1. Assessment of 24-hour Ambulatory Blood Pressure (ABP). We have experience measuring 24-hour ABP and will use the Oscar 2 ABP monitor (Suntech Medical Inc., Raleigh, NC), which has been validated by previous investigators (Goodwin, Bilous, Winship, Finn, & Jones, 2007; Jones, Bilous, Winship, Finn, & Goodwin, 2004). Clinic BP will be determined according to the new ACC/AHA guidelines (Whelton et al., 2018) with three readings taken after five minutes of quiet rest in a seated posture, each separated by 2 minutes, using the Oscar 2 BP monitor together with appropriate cuff size, and averaged to represent clinic BP. Subsequently, the ABP monitor will be programmed to take BP measurements every 20 minutes throughout the waking hours and every 30 minutes during the nighttime sleep period. We have used this procedure with excellent participant acceptability and compliance in numerous previous studies (Blumenthal, [name], & Gullette, 2000; Carels, [name], Szczepanski, & Blumenthal, 2000; Prather, Blumenthal, Hinderliter, & [name], 2011; [name] et al., 2011; [name], Thurston, Steffen, Blumenthal, Waugh, & Hinderliter, 2001). A successful 24-hour study will require at least 80% of the total readings to be valid, with no more than two consecutive hours lacking a valid reading (White et al., 2006). Unsuccessful ABP studies will be repeated.

In addition to mean 24-hour ABP, mean waking and nighttime ABP will be computed, with the nighttime sleep period defined by self-report and confirmed by actigraphy ([name] et al., 2001; [name] et al., 2011; [name] et al., 2002). Nighttime BP dipping will be defined as the percentage of the decline in nighttime systolic blood pressure (SBP) [(mean daytime SBP- mean nighttime SBP/mean daytime SBP) \times 100]; SBP dipping defined in this way is a continuous variable that will be a primary outcome measure in this proposed RCT. In addition, for descriptive purposes, a SBP dip \geq 10% will be classified as normal “dipper”, while $<10\%$ will be classified as “non-dipper”, with secondary analyses evaluating intervention effects on dipping status. Twenty-four-hour ABP assessments will be obtained at pre-randomization baseline, upon completion of the 8-week intervention, and at 6-month follow-up, in order to evaluate intervention effects on ABP and nighttime BP dipping.

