C.6.4. ASCVD – 10-Year Consensus Markers. We will collect demographic and clinical information required to characterize study participants' 10-year risk for ASCVD, and calculate it at baseline, post CBT-I, and at 6-month follow-up. The variables that are included in risk assessment equations are age, race, total and HDL-cholesterol, systolic BP (including treated or untreated status), diabetes, and current smoking status. Information on age, gender, race, and treatment of hypertension will be collected. Clinical information will be obtained from medical record review. Lipids and glucose levels will be determined from blood specimens drawn between 8:00-10:00 am following overnight fasting. All blood samples will be kept refrigerated until transfer to the appropriate laboratories. Lipids will be determined by enzymatic methods.

C.7. Risk/Benefit Ratio and Protections Against Risk

C.7.1. Study Risks. In both conditions, with regards to completing study measures, there is a risk of

discomfort or distress in answering questions, especially questions related to traumatic experiences. However, distress and discomfort related to questionnaire completion are usually temporary and well-tolerated. With the blood draw, there is a risk of bruising at the site of the draw and rarely, fainting and/or infection. There is a minimal risk of disrupted sleep associated with the sleep apnea assessment. The Oscar 2 ABPM has built in safe-guards to avoid over-inflation or prolonged inflation of the cuff, as well as a measurement abort key that can be activated by the participant. The FMD assessment will include blood pressure cuff inflation for 5 minutes, which has the risk of causing tingling and discomfort in the arm. There are no known risks associated with use of the actigraphy or the Qualtrics sleep diary. There is a potential risk associated with the loss of confidentiality of study data, although all due precautions will be taken to minimize such risk. Participants are provided information during the informed consent process about risks inherent with mobile app download and use, and use of a Duke-owned, loaned device.

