MLM can accommodate data missing at random, using maximum likelihood-derived estimates based on all available data. That said, data may be missing not at random (MNAR). That is, the outcome data may be systematically missing, for instance, from participants who experience no benefit from CBT-I. Nevertheless, even in the case of MNAR data, estimates derived from analyses examining Hypothesis 2 (addressing the within-person associations of change in insomnia with change in CVD risk) and the Supplemental Aim are unlikely to be affected by data missingness. After all, even if participants who benefit the least from CBT-I drop out of the study, we still anticipate observing the same magnitude of association between improved sleep and changes in cardiovascular biomarkers and QoL. By contrast, Hypothesis 1, which examines clinical response to CBT-I, would be affected by MNAR data. As such, we will conduct sensitivity analysis on three missing data approaches for Aim 1. First, we will conduct a completer analysis, analyzing only data from participants who complete each of the three assessments. Second, we will allow the maximum-likelihood estimation to generate estimates for all available data. In a third approach, we will use an intent-to-treat approach, assuming that missing post-intervention and/or 6-month follow-up data are evidence of stagnation. Specifically, we will use last observation carried forward in the cases of missing data.

D.3. Primary and Secondary Analyses

To examine the degree to which CBT-I is associated with improved sleep efficiency and insomnia severity index score (manipulation check), linear MLM will be used to model sleep outcomes as a function of treatment (CBT-I, control), time (baseline, post-intervention, 6-month follow-up), and the interaction between treatment and time. Planned treatment contrasts in change from baseline to post-intervention and 6-month follow-up will be examined within the context of the model. To determine the degree to which CBT-I is associated with improved CVD risk biomarkers (Hypotheses 1a), each of the 6 CVD risk variables (24-hr SBP, nighttime SBP dipping, FMD, 24-hr epinephrine, and norepinephrine) will also be modeled as a function of treatment, time, and their interaction, with planned treatment contrasts in change from baseline at post-intervention and 6-month follow-up. Dichotomized 10-year ASCVD risk scores (Hypothesis 1b) and QoL scores (Hypothesis 1c) will similarly be modeled via logistic MLM.

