To examine whether increased sleep efficiency is associated with decreased CVD risk (Hypothesis 2), lagged values will be used to create changes scores, defined by subtracting values for sleep efficiency and each of the CVD risk parameters measured at time $t-1$ from those measured at time t . Thus, decreases will be reflected by negative change scores and increases by positive change scores. Linear MLM will then be used to model each of the change scores corresponding to the 6 aforementioned CVD risk variables using the general equation below:

$$\text{CVD risk}_{\Delta t} = B0 + B1 * \text{Sleep efficiency}_{\Delta t} + B2 * \text{CVD risk}_{t-1} + B3 * \text{Sleep efficiency}_{t-1}$$

where change in the CVD risk outcome from $t-1$ to t will be modeled as a function of corresponding change in sleep efficiency, covarying for sleep efficiency measured at $t-1$ and the outcome in question measured at $t-1$. To explore the heterogeneity of CBT-I treatment response on sleep (Supplemental Aim), potential moderators (trauma type, insomnia phenotype, medication use, biological sex, and minority status) of the effect of CBT-I treatment on sleep outcomes will be examined via interaction effects. Specifically, sleep efficiency and sleep quality measured at baseline, post-intervention, and 6-month follow-up will be modeled in separate analyses as a function of treatment, time, a given moderator, and their second- and third-order interactions. To avoid the effects of multicollinearity, each moderator will be tested in a separate analysis. To determine whether the effect of changes in sleep efficiency on changes in CVD risk parameters vary by each of the aforementioned moderators, the analyses specified above for Hypothesis 2 will be modified to examine the main effect of a given moderator as well as the interaction effect of the moderator and sleep efficiency on each of the CVD risk variables.

D.4. Sample Size and Power Considerations

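### The arms are compared on 10-year ASCVD risk, a listed primary outcome, only as a dichotomised score, and quality of life is sent to a logistic model with no binary outcome defined

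*Combined protocol and SAP*

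**What the plan says.** **Hypotheses (Specific Aims, Aim 1).** Relative to control, CBT-I is expected to give "lower 10-year ASCVD risk score (Hypothesis 1b) and improved quality of life (Hypothesis 1c"). Both are worded as levels, not as the proportion of participants beyond a threshold.

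**Outcome status (C.1).** The primary outcomes are CVD risk biomarkers, "including flow mediated dilation, SNS activity, nighttime BP, nighttime BP dipping, and ASCVD risk". Quality of life is not on that list.

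**Analysis (D.3).** The treatment comparison for 1b and 1c is one sentence: "Dichotomized 10-year ASCVD risk scores (Hypothesis 1b) and QoL scores (Hypothesis 1c) will similarly be modeled via logistic MLM". It states no cut.

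**Candidate cut (ASCVD part of B.6).** The background text calls patients at elevated "risk if the Pooled Cohort Equations predicted risk is" 7.5% or more. Neither D.3 nor C.6.4 refers to it.

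**Availability (C.6.4).** The investigators will collect the inputs to the score "and calculate it at baseline, post CBT-I, and at 6-month follow-up".

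**Quality-of-life measures (C.5.1).** These are the SF-36, with physical and mental summary scores, and the WHOQOL-BREF. No responder definition is given, and no score is named as the test of 1c.

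**SBP dipping, for comparison (C.6.1).** "SBP dipping defined in this way is a continuous variable that will be a primary outcome measure in this proposed RCT". The 10% dipper category is descriptive, "with secondary analyses evaluating intervention effects on dipping status".

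**The concern.** The hypothesis concerns how far the risk score falls, but the planned model sees only which side of a line each participant is on. Someone whose risk falls substantially while staying above the cut, or who starts below it and improves further, contributes nothing to the comparison. A null result would then be hard to read: it could mean that CBT-I does not lower ASCVD risk, or that the dichotomy hid a real reduction.

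For quality of life the difficulty is one of definition. A logistic model needs a binary outcome and the plan supplies none. The score and the cut would have to be chosen later, possibly after the data are seen.

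**Working it through.** **1. Reproduce D.4.** Inputs from D.4: 150 participants (100 CBT-I, 50 control), three visits, ICC .50, 10% attrition at each later visit, two-sided alpha .05.

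A participant with m visits contributes m / (1 + (m − 1) × ICC) to the effective sample size (ESS).

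- No attrition: 150 × 3 / 2 = 225, as stated.
- With attrition, 121.5 participants have three visits, 13.5 have two and 15 have one: 121.5 × 3/2 + 13.5 × 2/1.5 + 15 = 215.25; D.4 states 215.
- ESS 215 split 2:1 is 71.7 control and 143.3 CBT-I. The standard error of a standardised difference is √(1/71.7 + 1/143.3) = 0.145. At d = 0.41, power is .809 by the normal approximation and .805 by the noncentral t; D.4 states 80%.

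The D.4 figure therefore reproduces, as a comparison of means on a continuous outcome.

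**2. Apply the same shift to a dichotomised score.** Assumptions not in the documents: the score is normal (or normal after log transformation), and a share p of controls lies above the cut. The cut is at c = Φ⁻¹(1 − p). Shifting the treated arm down by 0.41 SD leaves q = 1 − Φ(c + 0.41) above it. Power for two proportions is Φ[(p − q − 1.96 × SE₀) / SE₁], with SE₀ pooled and SE₁ unpooled.

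| Controls above cut, p (assumed) | CBT-I above cut, q | SE₀ | SE₁ | Power at ESS 215 |
|---|---|---|---|---|
| .50 | .341 | .0707 | .0711 | 61% |
| .30 | .175 | .0596 | .0628 | 55% |
| .20 | .105 | .0497 | .0538 | 48% |
| .10 | .045 | .0353 | .0395 | 36% |

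**3. Check the carried-over ESS.** A dichotomised variable is less correlated within person than its continuous parent. With an underlying correlation of .50, the binary correlations for the four shares are .33 / .32 / .30 / .25. Replacing ICC .50 by these values in step 1 raises the ESS to 254 / 258 / 265 / 280, and power becomes 69 / 63 / 56 / 43%. The loss is smaller but present at every share.

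**4. Quality of life: read the D.3 sentence both ways.** If the word dichotomised covers both outcomes, the quality-of-life cut is missing. If it covers ASCVD risk only, undichotomised scores go into a logistic model. Under either reading Hypothesis 1c cannot be analysed as written.

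**The case against.** **The cut is in the protocol.** B.6 defines elevated risk at 7.5% and no rival value appears. That stands. A reader might infer that the ASCVD cut is open to choice after the data are seen; the documents do not support this, because what is missing is a link from D.3 to B.6. Supplying the link would complete the definition but would not recover the discarded information.

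**A guideline category is a legitimate endpoint.** Also true. The logistic analysis is not invalid; it is inefficient, and it answers a different question from Hypothesis 1b.

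**ASCVD risk may be modelled linearly elsewhere.** Under Hypothesis 2, D.3 fits linear models to change scores "corresponding to the 6 aforementioned CVD risk variables", but names only five variables, so ASCVD risk could be the sixth. Even so, that model relates change in risk to change in sleep efficiency. It is not the randomised comparison.

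**SBP dipping sets no general rule.** It is tempting to say that D.3 breaks a protocol-wide principle that continuous forms are primary. C.6.1 speaks only of dipping. The fair statement is that two primary outcomes are handled differently and no reason is given.

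**The power figures are not estimates for this outcome.** Correct. The documents give no ASCVD mean, SD, within-person correlation, share above the cut or expected effect, and D.4 acknowledges that the effect of CBT-I on CVD risk is untested. The score also includes components, such as age, race and diabetes, that may move little in six months. The figures show what dichotomising costs under D.4's own assumptions, and no more.

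**Conclusion.** The concern holds. A listed primary outcome has its randomised comparison planned only as a dichotomy, against a hypothesis about a lower score. Hypothesis 1c has neither a named score nor a binary definition. These conclusions rest on the text alone.

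The size is illustrative. At d = 0.41, ESS 215 and unadjusted two-sided .05, about 80% power becomes 36% to 61% for an assumed 10% to 50% of controls above the cut, or 43% to 69% with the ESS recomputed for the binary outcome. Both ranges assume a normal score. D.4's 80% therefore does not describe the planned ASCVD analysis.

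A reader might extend the power criticism to quality of life. The documents do not support that: D.4's statement is about sleep and cardiovascular outcomes, and C.1 does not make quality of life primary. The quality-of-life fault is the undefined endpoint.

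This should be fixed; it does not undermine the trial as a whole.

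**What to change.** - **Hypothesis 1b:** make the main analysis a linear MLM on the continuous ASCVD score, on the log scale. Write the transformation into D.3 now, so that it does not depend on how the data look.
- **Hypothesis 1c:** name one continuous quality-of-life score and analyse it by linear MLM.
- **Contrasts:** for both, use the treatment-by-time contrasts already planned for Hypothesis 1a.
- **Secondary analysis:** keep ASCVD risk of 7.5% or more in logistic MLM, with the cut stated in D.3.
- **D.4:** state that the d = 0.41 figure does not apply to a dichotomised outcome.

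**Cost.** The clinical 7.5% category becomes secondary. A short amendment to D.3 and D.4 is needed, with IRB approval before implementation (C.7.5). No new data are required: the study measures table schedules ASCVD risk, the SF-36 and the WHO quality-of-life scale at baseline, post-treatment and 6 months, and linear MLM is already in the plan. The change should be made before outcome data are examined. The documents do not say whether that has already happened; if it has, the amendment should say so.

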- Insomnia among persons with PTSD is associated with increased physical health complaints (Clumb, Nishith, & Resick, 2011; Mohr et al., 2003), and is characterized by self-reported poor sleep quality, objectively measured short sleep duration, increased intermittent wakefulness, and decreased sleep efficiency.
- Insomnia persists following evidence-based PTSD treatments that have otherwise been successful in improving PTSD symptoms (Ohayon & Shapiro, 2000; Belleville, Guay, & Marchand, 2011).

- Our preliminary studies, as well as data from others (McCubbin et al., 2016), suggest that poor sleep is a significant mediator of the relationship between PTSD and CVD risk biomarkers.

Most of the previous work examining insomnia and CVD risk in individuals with PTSD has relied on cross-sectional designs, thus limiting the ability to establish a temporal relationship between PTSD sleep-related symptoms and CVD risk biomarkers. Despite compelling evidence of the link between insomnia and CVD risk, no studies have been specifically designed to examine the role that insomnia plays in the link between PTSD and CVD risk. Further, the current study provides a novel and innovative approach to assessing the direct effect of impaired sleep on CVD risk biomarkers. Since the majority of individuals with PTSD also meet criteria for co-morbid Insomnia Disorder (Talbot et al., 2014), we propose to use CBT-I to treat insomnia with the hypothesis that among those receiving CBT-I, improvements in sleep will result in improved diurnal blood pressure regulation and biomarkers of CVD risk compared to individuals receiving either sleep education alone or usual care. These findings would establish for the first time a direct link between insomnia symptoms (total sleep time [TST], wake after sleep onset [WASO], and sleep efficiency [SE]) and CVD risk among individuals with co-morbid PTSD and ID independent of other symptoms and health risk behaviors. The innovative use of CBT-I to specifically target CVD risk stands to make considerable contributions to research in other at-risk populations (e.g., depression). It is expected that insomnia treatment may be a novel and cost effective approach to reducing the CVD risk burden evident in this population.

B. RESEARCH STRATEGY: APPROACH

B.1. Insomnia and CVD risk

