Everyday Discrimination Scale	Participant	X ¹			
Short Form-36 Health Survey	Participant		X	X	X
Daily sleep diaries	Participant	X	X	X	X
Insomnia Severity Index	Participant	X ¹	X	X	X
Pittsburgh Sleep Quality Index with PTSD addendum	Participant		X	X	X

Epworth Sleepiness Scale	Participant	X ¹			
Medical Problems Checklist	Study coordinator ¹	X ¹			
STOP-BANG	Participant	X ¹			
Pre-Sleep Arousal Scale	Participant		X	X	X
Demographics measure	Participant	X ¹			
Fagerström Test for Nicotine Dependence	Participant	X ¹			
AUDIT-C	Participant	X ¹			
Leisure Time Exercise Questionnaire	Participant		X	X	X
Menopausal status	Participant		X		X
PEG	Participant	X ¹			
Medications List	Participant	X ¹	X	X	X
Insomnia Treatment Measure	Participant			X	Xau
Over-the-Counter Medications List	Participant	X ¹	X	X	X
Physiological Measures					
Actigraphy	Study staff ²		X	X	X
WatchPAT One sleep apnea assessment	Participant	X ²			
24-hour blood pressure assessment	Study staff ²		X	X	X
Flow mediated dilation	Study staff ²		X	X	X
24-hour urinary catecholamines	Participant ²		X	X	X
ASCVD risk	Study staff ²		X	X	X
Body Mass Index	Study staff ²		X	X	X

* Superscript 1 indicates that these procedures are completed at the first screen visit, and superscript 2 items are completed at the second screen visit.

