
C.5.4. Measurement of Other Potential Covariates. Menopausal status will be documented by self-reported menstrual bleeding, using the criteria described by Tom and colleagues (2010). Status categories are postmenopausal (natural or surgical), perimenopausal, and premenopausal. Menopausal status and lifetime alcohol use disorder (as well as current alcohol consumption measured as drinks per week) will be considered as potential covariates in analytic models. Pain will be measured with the 3-item PEG, a reliable and valid brief version of the Brief Pain Inventory (Krebs et al., 2009). For descriptive and analytic purposes, each patient's medications will be recorded and classified as: anticholinergic; alpha-adrenergic blockade; beta-blockade and other anti-hypertensive medications (diuretics, ACE inhibitors, and calcium channel blockers); specific serotonin re-uptake inhibitor (SSRI);

heterocyclic antidepressant; lithium; MAOI anti-depressant; other antidepressant; neuroleptic; or sedative-hypnotic. This classification system is based on our previous work involving the input and consensus of our team physicians ([name] et al., 2000).

C.6. Measures of Cardiovascular Disease Risk

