The Traumatic Stress and Health Research Laboratory (TSHRL) has established, IRB-approved standards of practice (SOP) for the evaluation of risk of suicide and homicide. All study staff members are trained in use of the psychiatric emergencies SOP by a Ph.D. or Masters' level clinician with years of experience in working with persons with PTSD. The SOP includes a thorough risk assessment including evaluation of risk factors and protective factors associated with both suicide and homicide. Also included in the policy are differential recommendations for action based on determinations of low, moderate, or high risk. Any staff member conducting an interview in which moderate or high risk is determined will contact a senior staff person with clinical expertise in risk assessment [including the PI, co-investigator(s), and/or DUMC's Emergency Room]. At several time points throughout the study, participants are reminded that they are asked to inform the study therapist, study coordinator, or study PI if they experience a psychiatric emergency such as homicidal or suicidal ideation. In addition, participants are provided the telephone number of study staff who they can call in the case of psychiatric emergencies, including an after-hours contact number.

C.7.7. Post-Study Referrals for Participants. It is not unexpected that participants in both conditions may complete the study with residual PTSD and/or major depressive disorder symptoms. Because participants complete the PTSD Checklist (PCL5) and the Beck Depression Inventory-II (BDI-II) at multiple time points, we will refer to these scores at the end of the study as a gauge of residual symptoms. We will provide referrals for continued treatment to anyone with a score of 38 or higher on the PCL5 and/or a BDI-II score of 20 or higher (i.e., moderate to severe depression range). Additionally, referrals will be provided to participants who self-report distress at symptoms of PTSD or depression

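### The Significance section promises a sleep–CVD link independent of other symptoms and health behaviours, but no model in Section D adjusts for changes in them

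*Combined protocol and SAP*

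**What the plan says.** Section A (Significance and Innovation) states the inference: "These findings would establish for the first time a direct link between insomnia symptoms" and CVD risk, "independent of other symptoms and health risk behaviors".

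D.3 gives one equation for Hypothesis 2. Change in the CVD marker between consecutive assessments "will be modeled as a function of corresponding change in sleep efficiency, covarying for sleep efficiency measured at" the earlier assessment, and for the marker's earlier value. It has no term for PTSD or depressive symptoms, exercise, smoking, alcohol, BMI or medication, and none for arm or visit. The Hypothesis 1 models contain treatment, time and their interaction. Medication use enters only as an exploratory moderator under the Supplemental Aim.

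C.5.4 says that menopausal status, lifetime alcohol use disorder and current drinking "will be considered as potential covariates in analytic models". It also covers pain (PEG) and medication classes. It names no model and no selection rule, and Section D does not take it up.

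Table 2 (Study Measures, in C.5) schedules the PTSD Checklist (PCL-5), BDI-II, "Leisure Time Exercise Questionnaire", medications and BMI at baseline, post-treatment and 6 months, although C.5.3 places BMI at the baseline lab visit. The "Fagerström Test for Nicotine Dependence", AUDIT-C and PEG are at screening only. Current smoking status is an input to the ASCVD score, which C.6.4 calculates at all three assessments.

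**The concern.** CBT-I is randomised; change in sleep efficiency is not. Within either arm, people whose sleep improves may also become less depressed, have fewer PTSD symptoms or exercise more, and any of these could move blood pressure dipping or FMD. Change scores remove stable differences between people but not factors that change along with sleep. An arm or visit term would not remove that confounding within arms.

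The protocol itself makes this plausible. B.6.2 links impaired FMD to depressive symptoms, anxiety and mental stress. B.6.1 cites stress and poor sleep as both contributing to blunted dipping. D.4 cites a stress-management programme, which is not a sleep treatment, as raising FMD with d = 2.32, and CBT-I in PTSD as improving psychosocial functioning with d = 1.02.

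The trial could therefore report a positive slope for sleep efficiency and attach the Section A conclusion to it, when the planned analysis cannot separate sleep from mood or behaviour.

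**Working it through.** **The plan's own figure.** D.4 assumes 150 participants, up to two change scores each and 10% attrition at each time point.
- 150 × 0.9 + 150 × 0.81 = 135 + 121.5 = 256.5, which agrees with the stated 256.
- D.4 then gives 80% power at β = .15. With Fisher's z, atanh(.15) × √253 = 0.1511 × 15.906 = 2.404, so two-sided .05 power is about 67% (regression t test: 67.7%). About 80% is reached one-sided (78.1% by the t test), or two-sided if the model explains roughly a quarter of outcome variance (78.8% at R² = .25). D.4 states neither condition for Hypothesis 2. The benchmark β = .15 is used below as given.

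**Size of a spurious slope.** All correlations are assumed; the documents give none for symptom or behaviour change. Suppose sleep has no effect, and an omitted change correlates r1 with sleep-efficiency change and r2 with CVD change. Leaving aside the lagged terms, the expected standardised slope is B1 = r1 × r2. The rejection rate is the probability that a normal variable with mean atanh(B1) × √253 and unit variance falls outside ±1.96. This treats the 256 change scores as independent, as D.4 does.

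| r1 | r2 | B1 | atanh(B1) × √253 | Rejection rate |
|---|---|---|---|---|
| .3 | .2 | .06 | 0.96 | 16% |
| .4 | .2 | .08 | 1.28 | 25% |
| .4 | .3 | .12 | 1.92 | 48% |
| .5 | .3 | .15 | 2.40 | 67% |

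The nominal rate is 5%. The regression t version gives 16% to 68% over the same range. In the last row the bias equals the β that D.4 aims to detect.

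**A milder range.** The nearest coefficients in the documents are those in D.4 for self-reported sleep disturbance, .18 and .11 in absolute value. They are not symptom-change coefficients and serve only as a guide to scale. Using them for r2:
- r1 = .3, r2 = .11: B1 = .033, rejection 8%.
- r1 = .4, r2 = .18: B1 = .072, rejection 21%.

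**Power cost of adjusting.** For a standardised slope, the squared noncentrality is n × β² × (1 − R²x) / (1 − R²). Here R²x is the share of variance in sleep change explained by the added covariates, and R² is the model's. With n = 256, β = .15, six added covariates (nine predictors) and two-sided .05:

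| Model R² | R²x = 0 | R²x = .1 | R²x = .2 | R²x = .3 |
|---|---|---|---|---|
| .0225 | 67.7% | 63.1% | 58.0% | 52.5% |
| .25 | 78.8% | 74.5% | 69.5% | 63.7% |

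The lost degrees of freedom cost almost nothing. The loss comes from overlap between the covariates and sleep change.

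**The case against.** The best reply concerns attribution. The independence sentence is background narrative and follows a sentence about CBT-I against comparison groups, so it may refer to the between-arm result. Hypothesis 2 is worded as an association throughout, and Section D never says its slope will show independence. A reader might infer that the analysis plan itself makes the claim for Hypothesis 2; it does not. The between-arm contrast would not support the phrase either, because it estimates the effect of CBT-I as a whole, including any effect on mood.

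A reader might also infer that all the relevant factors are measured at every visit. They are not: nicotine dependence, AUDIT-C and pain are at screening only. Nor is the plan silent on covariates, since C.5.4 names several and mentions pain and medication. The fair criticism is that none is committed to a model.

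The design also narrows the problem. Current alcohol or substance use disorder, concurrent trauma-focused therapy and unstable psychoactive or cardiovascular medication are exclusions, and randomisation is stratified by gender and smoking. None of this deals with symptoms that change during the trial.

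Finally, 67% is the top corner of an assumed grid and uses an uncorrected alpha, whereas D.1 applies a false discovery rate correction to Aim 2. That correction would lower the rejection rates, but it does not remove bias. Adjustment can also go too far: the Specific Aims call impaired sleep a hallmark PTSD symptom, so adjusting for PCL-5 change may remove part of the sleep effect.

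**Conclusion.** The concern holds in limited form. The plan as written cannot support a conclusion of independence from other symptoms and health behaviours, because no model in Section D adjusts for changes in them. That follows from the text and needs no assumption.

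The size does rest on assumptions. A spurious slope of .06 to .15 with 16% to 67% rejection needs correlations of .3 to .5 and .2 to .3. Correlations of .3 to .4 and .11 to .18 give about .03 to .07 and 8% to 21%. Both ranges assume 256 independent change scores and an unadjusted two-sided .05 test. The documents do not show that confounding of either size will occur, and these figures are not a forecast of the trial's error rate. The planned Hypothesis 2 model remains usable as a test of association.

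**What to change.** 1. Keep the planned Hypothesis 2 model.
2. Pre-specify beside it a sensitivity model that adds change and prior value of BDI-II, exercise and BMI, plus medication, smoking status and screening alcohol use. Confirm that BMI is taken at all three assessments, since Table 2 and C.5.3 differ. Smoking is a component of the ASCVD score, so it needs separate handling for that outcome.
3. Add PCL-5 change in a separate step. State that PTSD and depressive symptoms may be mediators as well as confounders, so that a smaller slope is not read as proof of confounding.
4. Report B1 with its interval from each model.
5. Describe Hypothesis 2 as an association. Limit any independence wording to the factors actually adjusted for, and only where B1 persists; otherwise delete the phrase from Section A. Independence from change in pain, or in drinking as measured by AUDIT-C, cannot be tested from measures scheduled only at screening.

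The cost is SAP wording and one or two further models per outcome; if BMI is taken as Table 2 shows, no new data collection is needed. The adjusted models have less power (for example 58.0% against 67.7% at β = .15 if the covariates explain 20% of sleep change and model R² is .0225), and they may over-adjust, which is why both sets of results should be shown.
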